Specifically, this study aims at predicting 2 target outcomes: acute exacerbations of COPD (AECOPDs) as defined by the GOLD initiative, and the CAT score as a proxy for patients' disease status. The start of an exacerbation within a patient, regardless of how many exacerbations the patient may have experienced before, will be predicted based on sensor data preceding the

exacerbation, and using basic covariates as well. For type of exacerbations, the severe and moderate exacerbations are considered as our main target as these are linked to the need of urgent medical intervention and will predict those as a group, but also separately (distinguish by type), if possible. Mild exacerbations, the relevance of which is currently a subject of investigation in the field, will also be explored.

For the CAT score, the aim is to predict the total score (max = 40) from the sensor data, and changes in the CAT score of ≥ 2 based on the MCID. With this approach, it is aimed to use the model built on sensor data as an objective means to reflect patients' disease status. While for the prediction of exacerbations the aim is to predict them as early as possible, i.e. days before an exacerbation, for the CAT/disease status prediction the aim is to reflect the daily status.

CCI

This study is exploratory in nature and any predictive models will need to be validated in future studies. A future remote patient monitoring (RPM) solution for patients with COPD built on these models will have 2 prime utilities: First, ameliorating or preventing exacerbations and their negative sequelae by early treatment intervention and second, to provide physicians and patients with a highly granular and precise view on the current disease status and past changes. Such information can be used by the treating physician to optimize therapeutic regimens and by the patients to accompany and optimize lifestyle changes. By using a multimodal sensor approach we intend to increase the accuracy of our predictive models beyond what has been described in the literature and thereby increase their clinical utility.

8 Research Question and Objectives

The aim of the study is to investigate the correlation of real-world sensor-derived biometric data obtained via a wearable device with clinical parameters and PROs for monitoring disease activity and predicting exacerbations for patients with COPD.

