9.5 Study Size

Sample size calculation is based on the second part of the primary objective, especially on predicting exacerbations of a severe or moderate type as outcome.

Assuming a desirable sensitivity and specificity of 0.85 for our algorithm and requiring that the lower 95% confidence limit should be at least 0.50 (with a probability of 0.95) for this exploratory approach, the number of observed exacerbation events needed is 18 ([Flahault 2005](#)).

Assuming that patients with COPD within our eligibility criteria (GOLD stage II-IV with a history of at least 2 moderate and/or severe exacerbations within any 12 month period within the last 3 years and at least 1 moderate or severe exacerbation within the last 12 months) show a frequency of 2 moderate or severe exacerbations per year, participants with COPD will have 0.5 events in 3 months (the in-study time). Further assuming that event occurrence over 3 months for every individual participant follows a Poisson distribution with parameter $\lambda = 0.5$, the number of events in the overall study population is also Poisson distributed and the corresponding parameter is the sum of individual parameters λ . Calculations show that a λ of 30 is needed to reach an upper cumulative distribution probability of 0.99 for observing at least 18 exacerbations. Therefore, 60 participants are needed to observe at least 18 exacerbation events within the 3-month observation period.

The events of interest in the context of the present study are COPD exacerbations (severe or moderate), exactly the onset of an exacerbation. For building the binary classifier predictive models we also require “no exacerbation” events. We will sample such events randomly from periods with no exacerbations, avoiding 2 weeks before and after an exacerbation.

Considering a drop-out rate of 10%, the estimated number is 67 participants with COPD that need to be included in this study.

This recruitment number is also in good agreement with published studies with regards to the ability to build predictive models for exacerbations. Studies with similar recruitment numbers ([Yañez 2012](#)) have been able to predict exacerbations based on single parameters studied. Strong features can compensate for low numbers in COPD machine learning model building as shown in

[Al Rajeh 2020](#), and using several features improves the accuracy of predictive models as seen in [Jensen 2012](#).

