9.9 Limitations of the Research Methods

- The data is collected from a very limited number of study sites in Germany. Hence the study population may not be representative of the population of patients with COPD. In addition, the fact that participation in the study requires cognitive capabilities to use applications and devices used for data collection in the study may cause selection bias towards a younger age group.
- Daily averages will be calculated to represent continuous measurements each day. There may be additional information encoded in smaller time periods (hour by hour or minute by minute) data or through defining bouts of activity.
- Some of the outcomes are based on subjective self-assessment e.g. COPD symptoms and health status will be assessed by the CAT score. In validation studies, the CAT score has been shown to be a valid and reliable tool to assess perceived health status (Jones 2013), though validity of the online version remains to be proven.
- The number of observed exacerbations will be low, and predictive models will need to be refined and validated in a larger population.

- Severe and moderate AECOPDs will likely be encountered in only ~40% of the participants with COPD. This may impact the generalizability of predictive models for AECOPDs.
- This study is a national study in Germany and will only recruit patients with sufficient proficiency in the German language. It is therefore impossible to assess potential bias in the gathered data and conclusions with regards to language, ethnicity, cultural background, country of origin, and social factors not encountered in the study population. This refers both to PROs and the interpretation of sensor data. Future studies will need to study these potential biases in a multinational setting.
- Mild exacerbations are captured via the labelling section in the patient facing application as “additional medication used” (self-reporting). Therefore, the capture of mild exacerbations depends on patients’ adherence to the intended application use and daily reporting. Mild exacerbations may therefore be under-reported (but also over-reported in case of erroneous entries).
- Participants may not adhere to the intended constant wearing or charging regimens of the device and therefore available data may have too many gaps to allow meaningful interpretation.

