			
 - Number of moderate or severe exacerbations prior to baseline visit (preceding 36 months, in case available) - Comorbidities at baseline - Current medication including COPD treatment at baseline - COPD severity (GOLD stage) 
Other covariates (Lung Function and Laboratory variables at Day 0, moderate/severe exacerbation visit and End of study visit) from the physician chart:
 
 - Body plethysmography parameters: FEV1 [L], FVC [L], FEV1/FVC, TLC [L] (total lung capacity), RV [L] (residual volume), FRCpleth [L] (functional reserve capacity), IC [L] (inspiratory capacity), Raw [kPa s L-1] (=ratio of sRaw to FRCpleth; airway resistance), sRaw [kPa s] (specific airway resistance), VT [L] (mean tidal volume), ERV [L] (expiratory reserve volume), IRV [L] (inspiratory reserve volume). - Blood gas analysis: (capillary) pO2 [mmHg], O2 [%] saturation and pCO2 [mmHg] - Serum CRP [mg/l] and serum procalcitonin levels [ng/ml] - Blood count (CBC with differential); only values that are available with routine blood counts: Hb [g/dL], Hct [%], Erythrocyte count [$10^6/\mu\text{L}$], MCV [fL], MCH [pg], MCHC [g/dL], Reticulocytes [$\times 10^3/\mu\text{L}$] [% (of erythrocytes)], RDW [], platelet count [$10^3/\mu\text{L}$], WBC count [$\times 10^3/\mu\text{L}$], Lymphocytes [$\times 10^3/\mu\text{L}$] [%], Monocytes [$\times 10^3/\mu\text{L}$] [%], Neutrophils [$\times 10^3/\mu\text{L}$] [%], Eosinophils [$\times 10^3/\mu\text{L}$] [%], Basophils [$\times 10^3/\mu\text{L}$] [%]

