- If the overlapping exacerbations have different types, the start date will be the start date of the first moderate or severe exacerbation, and the end date is the end date of the last moderate or severe exacerbation.

The following exacerbation-related outcomes are required for the analysis of primary objectives:

1. Time points (start and end dates) of mild/moderate/severe exacerbations for descriptive analysis of sensor variables (see Section 2.1.4)
2. Occurrence of moderate/severe exacerbations as binary outcome measured at the onset date of an exacerbation for predictive analysis. An event is the occurrence of a moderate/severe exacerbation. Non-exacerbation events (for definition see Section 1.3.2) will be sampled randomly from time points (days) outside of exacerbation periods (defined by start and end dates of each exacerbation) and avoiding 2 weeks before the onset time (day) and two weeks after the end time (day) of an exacerbation.

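### Primary objective 2: control days are sampled with no link to participant, so pooled sensitivity, specificity and AUC mix who is at risk with when an exacerbation starts

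*SAP*

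**What the plan says.** SAP 2.3.1 takes the onset day of a moderate or severe exacerbation as the event. Control days "will be sampled randomly from time points (days) outside of exacerbation periods", "avoiding 2 weeks before the onset time (day) and two weeks after the end time (day) of an exacerbation". Protocol 9.5, repeated in SAP 1.3.2, gives the same rule: "We will sample such events randomly from periods with no exacerbations, avoiding 2 weeks before and after an exacerbation". Neither document matches or stratifies control days by participant, or says how many are drawn.

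The aim is in Protocol 7: "The start of an exacerbation within a patient, regardless of how many exacerbations the patient may have experienced before, will be predicted based on sensor". The rest of that sentence makes clear that the readings meant are those from before the event, and it names basic covariates as a further input. The objective 2 variables in Protocol 14.1.2 include GOLD stage, comorbidities, medication and "Number of moderate or severe exacerbations prior to baseline visit (preceding 36 months, in case available"). SAP 3.4.2 lets every available feature into the predictive models.

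SAP 3.4.5.2 assesses performance by accuracy, sensitivity, specificity, AUC and related metrics over the COPD cohort, with internal cross-validation. It plans no covariates-only comparison and no within-participant metric. Protocol 9.9 expects that "Severe and moderate AECOPDs will likely be encountered in only ~40% of the participants with COPD", and treats this as a limit on generalizability.

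**The concern.** Event days can come only from the minority of participants who exacerbate during follow-up. Control days come mostly from the others: an event-free participant offers every day, while each event removes its own duration plus up to 28 days from the participant who had it. Event and control days then differ by person as well as by time. Any feature that marks a higher-rate participant helps to separate them, even if the sensors change not at all before onset.

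Cross-validation does not remove this, and neither would folds grouped by participant, because a prognostic trait carries over to new people. What is at stake is interpretation. The models are meant as the basis for a remote monitoring product that warns days ahead. From the pooled metrics alone, the sponsor could not tell how much of the performance is sensor warning and how much is baseline risk.

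**Working it through.** **Inputs.**
- Rate, from Protocol 9.5: "participants with COPD will have 0.5 events in 3 months (the in-study time"), where "event occurrence over 3 months for every individual participant follows a Poisson distribution with parameter" 0.5.
- 60 evaluable participants (Protocol 9.5).
- Buffer of 14 days before onset and 14 days after the end (SAP 2.3.1).
- Follow-up of 3 months, taken as 90 or 91 days.
- Episode duration: no figure in the documents. Assumed 8 or 10 days, range 1 to 21.
- Variation of rates between participants: no figure in the documents. Assumed gamma with mean 0.5 and shape 2 or 1, besides the plan's common rate.

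**The plan's own figures reproduce.** P(X ≥ 18 | λ = 30) = 0.993, against the stated 0.99. 60 / 0.9 = 66.7, so 67. Share of participants with an event: 1 − exp(−0.5) = 39.3%, against the stated ~40%.

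**Where the control days come from** (common rate, 90 days, 10-day episodes).
1. Participants without an event: 60 × exp(−0.5) = 36.4. They supply 36.4 × 90 ≈ 3,275 eligible days.
2. Participants with an event: 60 − 36.4 = 23.6. Each event blocks 14 + 10 + 14 = 38 days, fewer at the ends of follow-up. Simulation with uniform onsets leaves 50.9 eligible days per participant, so 23.6 × 50.9 ≈ 1,202 days.
3. Share from event-free participants: 3,275 / (3,275 + 1,202) = 73%.

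| Setting | Share from event-free participants |
|---|---|
| Common rate, 1-day episodes | 71% |
| Common rate, 10-day episodes | 73% |
| Common rate, 21-day episodes | 76% |
| Gamma shape 2 / shape 1 (91 days, 8-day episodes) | 76% / 78% |
| 0.25 / 1.0 events per 3 months instead of 0.5 (10-day episodes) | about 85% / 54% |
| Equal number of days drawn per participant, common rate | 61% |

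**What baseline risk alone can score.** Let the score be the participant's true rate, with no sensor information. Ignoring the buffer, rates follow Gamma(k) over control days and Gamma(k+1) over events, because people contribute events in proportion to their rate. Then AUC = P(Gamma(k+1) > Gamma(k)):
- k = 1: 1 − (1/2)² = 0.75
- k = 2: P(at least 2 heads in 4 fair tosses) = 11/16 = 0.69
- one common rate: 0.50

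Simulation with the SAP buffer and 5-day merging (91 days, 8-day episodes) gives 0.71 for shape 2 and 0.77 for shape 1. Replacing the true rate by a 36-month event count, which the model does receive, gives 0.68 and 0.75. An approximate filter for inclusion criterion 4 lowers these to 0.63 and 0.68. The filter also raises the mean rate above 0.5, and the event-free share of control days becomes 67-70%.

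**What a within-participant comparison does.** A feature that is constant over time ties on every comparison, so its AUC is 0.50 by construction. Data suffice: with 10-day episodes a participant with an event has about 51 eligible control days on average. About 0.3% of events fall in participants with no eligible day, rising to about 2% with 21-day episodes.

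**The case against.** **Covariates are a declared input.** Objective 2 asks for a model using sensor data together with demographic and medical covariates. A reader might infer that person-level risk is leakage and that the headline control days must be matched to the same participant. The documents do not support that. A monitoring tool runs on all patients, and false alarms in event-free patients belong in its specificity. Matched controls would condition on a future outcome, drop about 60% of participants and stop measuring the covariate part of the model. This objection stands, and it is why the all-participant analysis should remain the main result.

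**The size is assumed.** Under the plan's single Poisson rate the excess is nil. A reader might infer that baseline risk alone could meet the target of 0.85 for both sensitivity and specificity. At the shapes tried it does not. Even the true rate reaches only about 0.65-0.66 (shape 2) or 0.70-0.71 (shape 1) when the two are equal. At sensitivity 0.85 its specificity is about 0.41-0.42 or 0.52-0.55. Eligibility also narrows the range of risk. This stands as a limit on size. It does not remove the point, since history and GOLD stage are useful predictors only if risk differs between people.

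**Event-free is not exacerbation-free.** A reader might take the 73% as people who never exacerbate. Inclusion criterion 4 requires a history of moderate or severe exacerbations; the figure concerns only the 3 months of observation.

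**Partial safeguards exist.** Protocol 9.3 allows each participant's Day 8-14 values as a reference for change or as a model co-factor. Protocol 9.7.2.1 will explore how the metrics depend on the time before onset. SAP 3.4.5.2 plans Shapley values and similar explanatory methods. The study is exploratory, with validation left to future studies. These help a careful reader, but none gives the increment from sensors over baseline covariates, or a performance figure within participants.

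**Conclusion.** The point holds as one of interpretation. The sampling rule does not separate participants, and the planned metrics pool over them, so by themselves they cannot show the within-patient timing signal named in Protocol 7. The share of about 73% assumes uniform sampling from pooled eligible days at the plan's rate, with an assumed episode duration. The AUC of 0.71 to 0.77 assumes gamma-distributed rates that the documents do not give, and a score that knows each true rate. It is an illustration of what baseline risk could contribute, not a forecast. The documents do not show that a good AUC would reflect baseline risk only, and the sample size is unaffected.

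**What to change.** Keep the all-participant analysis of objective 2 as the main result. In SAP 3.4.5.2 add beside it:

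- **(a)** the same metrics for a model with Day 0 covariates only, so that the increment from sensor data is visible;
- **(b)** a within-participant AUC that compares each event with eligible control days of the same participant.

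Base any statement about early warning from sensors on (a) and (b). In SAP 2.3.1, also state whether control days are drawn from the pooled days or in a fixed number per participant, since at the plan's rate this moves the event-free share between about 73% and 61%.

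The cost is SAP wording and a little programming, with no new data. The downside is that (b) rests on about 24 of 60 participants, so it will be imprecise and may look less favourable than the pooled result.

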	
 Self-reported activities (e.g., coughing, sports, sleeping) as collected by the participant app Self-reported satisfaction to the study, collected via end of study questionnaire 
Covariates will be collected from patient records (status at the time of Day 0, closest record prior to):
 
 Demographics, Body mass index, Smoking status Relevant medical history, comorbidities, current medication including COPD treatment at baseline Date of diagnosis of COPD and COPD severity (GOLD stage) Number of moderate or severe exacerbations prior to baseline visit (at Day 0, moderate/severe exacerbation visit and End of study visit): Current body plethysmography parameters Current (capillary) pO₂, O₂ saturation and pCO₂ 
Several biomarkers at the time of baseline depending on availability

Data Sources	
The data source used for this study will consist of patients charts from 11 sites (mainly pulmonology private practices) in Germany as well as from a device, which will get handed out to the participant.
 
The data informing this study will be extracted from patient medical records using eCRF directly in an electronic data capture system. In addition, a patient reported outcomes (PRO) questionnaire (COPD assessment tool [CAT], filled in by the participant electronically), and a wearable device (adhesive patch device with sensors) will be used for data collection.

Study Size	
Sample size required to show a sensitivity of ≥ 0.85 for a model predicting moderate to severe COPD exacerbations was estimated to be 67 participants including a drop-out rate of 10%. The study will also observe 10 participants in the calibration cohort for 2 weeks. The number of participants for this cohort is chosen on an exploratory basis.

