9.1.2.1 Primary Outcomes

The primary objective is to 1) describe the distribution of sensor collected data with COPD exacerbations, as well as 2) to predict COPD exacerbations by building a statistical model.

Severity of acute exacerbations of COPD (AECOPD) are defined using the GOLD definitions based on treatment consequences (event-based) ([Vogelmeier 2017](#)): AECOPDs are defined as “an acute worsening of respiratory symptoms that results in additional therapy”. Exacerbations are classified as 1) **mild** if they are treated with short-acting bronchodilators only; 2) **moderate** if they are treated with short-acting bronchodilators plus antibiotics and/or oral corticosteroids; or 3) **severe** if the patient visits the emergency room or requires hospitalization because of an exacerbation.

The occurrence of exacerbations during the observation period will be defined as follows:

- For moderate/severe exacerbation requiring a physician’s intervention, emergency room visit or hospitalization, the severity, date of the exacerbation, and the duration of the exacerbation will be recorded via an eCRF.
- For mild exacerbations: self-reported; treated by the participant without intervention by a physician will be documented in the patient application labeling section (days with added treatment).

The duration of exacerbations during the observation period will be defined as follows:

The duration of a severe/ moderate exacerbation will be derived from the duration of added medication from the group of systemic corticosteroids and/or antibiotics which define moderate exacerbations by GOLD. Days in-hospital for severe exacerbations will also be captured.

The duration of mild exacerbations will be derived from the event “additional relieve medication taken” noted in the labelling section of the patient facing applicaton (which defines mild exacerbations). Duration and start / stop will be derived from these patient entries.

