9.10.3 Monitoring

A CRO will perform monitoring according to the study's Monitoring Plan. Investigators need to ensure that the Monitor has access to relevant documents during monitoring visits and that they and/or relevant site staff members are available to discuss any issues that may arise.

Recruitment rates and exacerbation frequency in the COPD study population will be reviewed in 2-week intervals to compare against assumptions and allow for timely adjustments of the study protocol and conducting sites to reach the projected minimum number of moderate or severe exacerbations (n=18). Participants will be instructed to inform any physician outside of this study of their participation in this study and the need to inform the respective PI on relevant medical events and exacerbations.

The study monitor will send monitoring reports to the Sponsor.

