## 2.3 OUTCOME DEFINITIONS

### 2.3.1 Outcomes for primary objectives

The primary outcomes are based on COPD exacerbations. Exacerbations are classified as

- 1) mild if they are treated with short-acting bronchodilators only,
- 2) moderate if they are treated additionally with antibiotics or oral corticosteroids, or
- 3) severe if the patient visits the emergency room or requires hospitalization because of an exacerbation.

The occurrence of exacerbations during the observation period is measured as follows.:

- For moderate/severe exacerbation requiring a physician's intervention, exacerbation details will be recorded via eCRF by the clinical site. Severity, onset and duration will be derived according to the definition above from the documented COPD medication associated with the patients' exacerbation visit. The definition details for COPD medication and ATC codes will be finalized during the planned Data review meeting prior to the final analysis.
- For mild exacerbations: self-reported; treated by the participant without intervention by a physician will be documented in the patient application labeling section (days with added treatment: short-acting bronchodilators only). The start date and end date of addition of short-acting bronchodilators can thus be retrieved from the patient application. The documented use of additional medication (Bedarfsmedikament) will be considered as a mild exacerbation with the following rules for start and end days:
  - A mild exacerbation must start with at least 2 consecutive days of additional medication reported, the first day of consecutive medication will determine the start of the exacerbation.
  - If there are gaps in the additional medication reporting, a maximum of 2 days is allowed to be considered only one exacerbation. A minimum of 70% of the days must have additional medication reported. The end date of the exacerbation is the last day where both these rules are fulfilled.
- Any exacerbations that happen within 5 days will be considered as overlapping, as well as exacerbations that have an intersection in their start and end dates. Overlapping exacerbations will be considered as only one and classified as the graver one. (4)
  - If all overlapping exacerbations have the same type, the start date is the start date of the first exacerbation, and the end date of the last one.

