### 3.4.5 Analysis of outcomes

#### 3.4.5.1 Primary Objective 1

Descriptive statistics will be reported in terms of mean (SD) or median (IQR) for continuous variables, as well as counts and frequency (%) for categorical variables of sensor collected data described in section 2.1.4, comprised of

- physical activity,
- heart rate,
- resting heart rate,
- heart rate variability (10 variables),
- temperature,
- respiration rate,
- ratio of in- vs. expiration time
- cough frequency,
- sleep pattern (hours of sleep),
- frequency of additional medication

measured for each patient

1. at baseline (Day 0),
2. in the period Day 8 to Day 14 (intra-individual period average),
3. from 14 days prior to an exacerbation onset, in a 7-day sliding time window, in a 3-days sliding time window, and a 1-day sliding time window,
4. at the onset of an exacerbation (first day of exacerbation period),
5. from the end of an exacerbation to 14 days after, in a 7-day sliding time window, in a 3-days sliding time window, and a 1-day sliding time window,
6. 14, 21, and 28 days after an exacerbation.

The analysis will be repeated for different exacerbation severities:

1. Exacerbations of any (moderate or severe) severity are counted
2. Only severe exacerbations are counted
3. Only moderate exacerbations are counted
4. Only mild exacerbations are counted

Results will be reported in one table per parameter, with descriptive statistics indexing rows and measurement times indexing columns.

For each continuous parameter, mean values will be plotted across all daily measurement time points during the 3-month observation period, together with 95% CIs based on the normal approximation (t-statistic).

### 3.4.5.2 Primary Objective 2

To predict moderate or severe COPD exacerbations by building a statistical model employing sensor-derived data and demographic and medical covariates.

To generate several features needed as input to the model a number of algorithms (e.g., self-learning algorithms) for obtaining derived parameters such as cough frequency, physical activities and sleep pattern will be developed first using the label dataset obtained via the app (see Section 3.4.3).

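### Control days for the exacerbation model are not balanced by day of week, while onset dates may cluster on working days, so the calendar alone could modestly inflate the objective 2 metrics

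*SAP*

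**What the plan says.** **Event days.** For objective 2, SAP 2.3.1 (item 2) takes the onset date of a moderate or severe exacerbation as the positive instance. On how that date is obtained, the same section says: "Severity, onset and duration will be derived according to the definition above from the documented COPD medication associated with the" exacerbation visit. The medication definitions are left to a data review meeting. Protocol 9.1.2.1 says that "the severity, date of the exacerbation, and the duration of the exacerbation will be recorded via an eCRF", without stating whether that date is first symptoms, first dose or the visit.

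**Control days.** These "will be sampled randomly from time points (days) outside of exacerbation periods". The only other restriction is a buffer of two weeks before onset and two weeks after the end of an exacerbation. SAP 1.3.2 and Protocol 9.5 describe the same sampling.

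**Setting and predictors.** The Data Sources entry of the Protocol abstract (section 4) describes the sites as "mainly pulmonology private practices". SAP 3.4.2 lets all available features into the predictive models. SAP 2.1.4 lists among these physical activity, heart rate, hours of sleep and time-stamped bed and wake logs.

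**Day of week.** Neither document matches, stratifies or adjusts for it.

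**The concern.** Event days and control days are selected by different calendar mechanisms. Moderate events are defined by antibiotics or oral corticosteroids, which Protocol section 7 says need a physician's involvement, so the recorded onset follows access to care. Control days follow the calendar evenly. If onsets cluster on working days and the sensor variables have a weekly rhythm, a classifier can gain some accuracy by telling working days from weekends.

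Two features of the plan make this worth attention. First, Protocol 9.7.2.1 will explore how model metrics depend on the time before an exacerbation. A calendar artefact changes with lead time and returns every seven days, so it could be read as an early-warning pattern. Second, the internal cross-validation in SAP 3.4.5.2 cannot reveal it, because every fold shares the same sampling rule. Drawing controls from the same participant would not remove it either. Recognising the calendar has no value for the monitoring tool that these models are meant to support.

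**Working it through.** **The plan's own figures.** With true sensitivity 0.85 and an exact one-sided 95% lower limit of at least 0.50, the smallest number of events is 18: at least 13 must be detected, which has probability 0.958. For a Poisson mean of 30, P(at least 18 events) = 0.993. Then 30/0.5 = 60 participants, and 60/0.9 = 66.7, rounded up to 67. These figures reproduce, and none depends on how control days are sampled.

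**Inputs.** Control days fall on working days with probability 5/7 = 0.714 and at weekends with probability 2/7 = 0.286 (SAP 2.3.1, random sampling). The share *w* of onsets on working days is not in the documents. It is an assumption, shown from 0.714 (no clustering) to 1.00.

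**Onset day, perfect recognition of weekends.** A rule that only recognises working days has sensitivity *w*, specificity 2/7 and AUC = 0.5 + (*w* - 5/7)/2.

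| *w* | Sensitivity | Specificity | AUC |
|---|---|---|---|
| 0.714 | 0.714 | 0.286 | 0.500 |
| 0.80 | 0.800 | 0.286 | 0.543 |
| 0.90 | 0.900 | 0.286 | 0.593 |
| 1.00 | 1.000 | 0.286 | 0.643 |

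**Before onset.** Protocol section 7 predicts from data preceding the exacerbation, so the lead time matters. Take *w* = 1 with onsets spread evenly over Monday to Friday. For a single day the ceiling is 0.5 + |weekend share before events - 2/7|/2.

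| Data used | Weekend share before events | Calendar-only AUC |
|---|---|---|
| Day -1, day -6 | 1/5 = 20% | 0.543 |
| Days -2 to -5 | 2/5 = 40% | 0.557 |
| Day -7, day -14 | 0% | 0.643 |
| 3 days before onset | number of weekend days: 0 in 40%, 1 in 20%, 2 in 40% (controls 43%, 29%, 29%) | 0.571 |
| Full 7-day mean | always 2 of 7 days | 0.500 |

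With *w* = 0.90 the ceiling is 0.528 at day -1 and 0.546 for the 3-day window.

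**Partial recognition.** If a sensor score separates working days from weekends with AUC *A*, the spurious AUC is 0.5 + (*A* - 0.5) × (difference in working-day share). For *A* from 0.6 to 0.8 (assumed):
- Day -1 (0.800 against 0.714): 0.5 + 0.1 × 0.086 = 0.51 to 0.5 + 0.3 × 0.086 = 0.53.
- Onset day, day -7 or day -14 (1.000 against 0.714): 0.5 + 0.1 × 0.286 = 0.53 to 0.5 + 0.3 × 0.286 = 0.59.

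**After matching.** If control days have the same weekday distribution as onset days, the days before them do too, whatever the lag. The calendar-only AUC is then 0.500 at every lead time.

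**The case against.** A reader might infer that onsets fall almost only on working days and that the metrics are therefore raised. The documents do not support that:
- An exacerbation is "severe if the patient visits the emergency room or requires hospitalization because of an exacerbation", and such contacts are not tied to practice hours.
- Physicians outside the study may treat events; Protocol 9.10.3 has participants tell them of "the need to inform the respective PI on relevant medical events and exacerbations".
- Protocol Table 4 lets a visit record events that occurred since Day 0, so dates can be entered afterwards.
- Medication associated with a visit need not start on the visit day.
- Sites may include outpatient hospital settings (Protocol 9.1.1) and academic or referral centres (Protocol 9.4).

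Clustering is plausible, but no figure for it exists.

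Nor should 0.64 be read as the expected inflation. It is a ceiling for a calendar-only rule, not an amount added to a model that has real signal. With specificity 0.286, such a rule cannot reach the 0.85 target by itself. An excess of Mondays does not simply strengthen the case: if all onsets are on working days and 2/7 of them are Mondays, the day before onset is a weekend day exactly as often as for controls, and the AUC for that day is 0.50.

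A reader might also conclude that the short windows in objective 1 are misleading and should be dropped. SAP 3.4.5.1 reports them "in a 7-day sliding time window, in a 3-days sliding time window, and a 1-day sliding time window", so a whole-week summary stands beside them. The 1-day series before onset covers 14 days, so a pure weekly rhythm would repeat after seven days.

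Finally, the study is exploratory, its models need later validation, and random error is large: with 18 events and an assumed 180 control days, the standard error of an AUC near 0.52 is about 0.07. This argues for a small change, not for none. The artefact is systematic, and the change is nearly free.

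**Conclusion.** The point holds as a conditional, modest bias. Onset dating may favour working days, control sampling does not, and nothing in the plan balances the two. With onsets spread evenly over Monday to Friday and perfect weekend recognition, the calendar-only AUC would be 0.64 on the onset day and at days -7 and -14, 0.54 to 0.56 on the other single days of the week before onset, 0.57 for the 3-day window, and 0.50 for a whole-week mean. Weekend onsets or partial recognition reduce it, and an uneven spread within the working week would change the pattern across lead times. The feature windows for objective 2 are not specified, so the documents do not settle which row applies. The share of weekend onsets and the strength of the weekly rhythm are unknown; in a largely retired cohort the effect would probably be at the lower end.

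**What to change.** In SAP 2.3.1 (item 2) and SAP 1.3.2, state that non-exacerbation days are sampled stratified by day of week, so that their weekday distribution matches that of the onset days. Add a table of the weekday distribution of moderate and severe onsets, so that readers can see whether clustering occurred.

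In objective 1, keep the planned 1-day and 3-day windows and read them beside the 7-day windows already planned. Re-expressing or dropping the short windows would be a larger trade-off and is not needed.

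The cost is a sentence in each SAP section, one stratification step in the sampling code and one small table. The downside is a somewhat smaller pool of eligible control days. It stays large: Protocol 9.9 expects about 40% of participants to have a moderate or severe event, so of 60 participants about 36 would have none. Taking 3 months as about 13 weeks, that gives 36 × 13 = 468 candidate days for each weekday, before allowing for missing sensor data and mild exacerbations. The number of events and participants does not change.
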